Specific Aim I: To determine whether implementation of COVID-19 booster vaccine trusted messaging platforms is associated with increased booster vaccine uptake in vaccinated ED patients. At five EDs (Zuckerberg San Francisco General, UCSF Parnassus Medical Center [San Francisco, CA], Thomas Jefferson University Hospital [Philadelphia, PA], Ben Taub Hospital [Houston, TX], Duke University Medical Center [Durham, NC]), we will conduct a cluster-randomized controlled trial of the implementation of PROBOOSTVAXED trusted messaging platforms, with 30-day booster vaccine uptake as the primary outcome and booster vaccine uptake in the ED as a secondary outcome. *Hypothesis: Implementation of PROBOOSTVAXED trusted messaging platforms in EDs will be associated with increased 30-day booster vaccine uptake in vaccinated ED patients.*

Specific Aim II: To determine whether implementation of COVID-19 booster vaccine trusted messaging platforms in EDs is associated with increased booster vaccine acceptance in vaccinated ED patients. For this specific aim, booster vaccine acceptance in the ED assessed via ED survey will be the primary outcome. *Hypothesis: Implementation of PROBOOSTVAXED trusted messaging platforms in EDs will be associated with increased booster vaccine acceptance in vaccinated ED patients*.

Specific Aim III: To determine whether implementation of a protocol in which ED patients are asked whether they will accept a COVID-19 booster vaccine in the ED is associated with increased booster vaccine uptake in vaccinated ED patients. Hypothesis: Implementation of an ED protocol in which patients are asked whether they will accept a COVID-19 booster vaccine will be associated with increased 30-day booster vaccine uptake in vaccinated ED patients.

General Design: This is a three-arm cluster-randomized controlled trial (CRCT) to accomplish Specific Aims I, II, and III.

Study arms

PROBOOSTVAXED Intervention M	Intervention Q (Vaccine Question,	Control (No Messaging, No
(Messaging + Vaccine Question)	No Messaging)	Vaccine Question)

- Vaccine messaging given
- Vaccine acceptance question asked
- No vaccine messaging
- Vaccine acceptance question asked
- No vaccine messaging
- No vaccine acceptance question

Primary Outcome for Specific Aims I and III: Booster Vaccine Uptake in the ED

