Introduction to ED Staff: Clinical Research Coordinators (CRCs) will set up their workstation in the ED and introduce themselves to ED staff (nurses, physicians, and mid-levels), informing them that they will be doing the PROBOOSTVAXED study that day. **They will avoid telling providers whether this is an intervention versus control arm.**

Initial Screening and Scripted Consent for Surveys: CRCs will review ED dashboards for inclusion and exclusion information. When an eligible patient is identified, the CRC will ask the nurse or doctor caring for the patient whether it is okay for them to approach the patient about the study. For provider approved patients: CRCs will approach eligible patients and deliver a scripted consent for two short surveys – the Intake Survey and the (Post-Intervention) Vaccine Acceptance Survey. See Scripted Consent for the No Messaging arm period.

CRCs will complete screening and enrollment log indicating whether or not they agreed to participate. If they agreed to participate, the CRC will assign a Study ID#.

Intake Survey: We will administer the INTAKE SURVEY to participants. CRCs will have the option of inputting surveys to REDCap on iPads in real time or using paper surveys (and later inputting into REDCap). These surveys are to be delivered orally (CRC asks questions), not via handing them out. The Intake Surveys are the same for all three arms of the study.

Primary and Other Outcome Ascertainment: Ascertainment of primary and secondary outcomes will occur in the same manner as in the intervention arms.

XI. Research Staff Informing ED Providers When Participants Will Accept COVID-19 Booster Vaccine for Intervention M and Intervention Q Arms

Only some study site EDs will have the capability of administering COVID-19 booster vaccines during the initial ED visit. The last question in the Vaccine Acceptance Survey **in both the Intervention M and Intervention Q arms** of the study is "Would you accept the COVID-19 booster vaccine in the emergency department today if your doctor asked you?" For study site EDs capable of administering the COVID-19 vaccine, when a participant says they will accept the vaccine, the CRC or research staff will ask the participant if it is okay to notify that participant's ED provider(s) – nurse and/or physician that they said they will accept the vaccine

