and confirm whether or not they receive it in the ED. Research staff will not tell patients that they qualify for the booster vaccine and will not advise them in any manner. They will, however, inform the patient that if they choose to accept the vaccine, they may be liable for the vaccine's cost, depending on their medical insurance coverage. If participants agree to notification of the ED provider, research staff will notify the ED provider that they stated they will accept the vaccine. They will not tell the provider that they meet criteria for the booster vaccine and will not push that they get vaccinated.

XII. Consents and Rationale

We will obtain scripted verbal consent for Intake surveys in the same manner that we have conducted with the PROCOVAXED study, which is nearly identical in design and scope. We will obtain written HIPAA consent for EHR review and separate written consent for 30-day follow-up phone calls.

With regards to consent for delivery of the messaging intervention, we must emphasize that messaging for vaccine hesitancy is firmly a part of standard best-practice emergency department care (messaging of this type is currently be enacted in EDs across the US). Delivery of the vaccine messaging platforms is therefore an accepted common best practice not requiring consent. To add an extra layer of consent could lead to even greater vaccine hesitancy. We therefore plan the following processes with verbal assent for the Intervention:

- 1) At the end of the Intake Survey, asking patients if they are willing to watch a booster vaccine messaging video(s). If the patient says Yes, then we will play the video. If the patient says No, we will not play the video.
- 2) Asking participants whether they are willing to read an informational flyer about booster vaccines. If the patient says *Yes*, then we will give them the flyer. If the patient says *No*, we will not give them the flyer.
- 3) Handing the participant's ED provider(s) the scripted message about booster vaccines to deliver to the participant. Research staff will not mandate or check with providers whether they deliver the message.

XIII. Primary Outcomes and Ascertainment Primary Outcome and Ascertainment of Specific Aim I

Our primary outcome for Specific Aim I is 30-day booster vaccine uptake, **comparing the Intervention M arm versus the Control (No Messaging, No Vaccine Acceptance Question) arm**.

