CRCs will keep a running log of all study flow and enrollment, recording the following data for all patients approached: study date, study arm, "Yes" and "No" agreeing to surveys, delivery or non-receipt of messaging platforms, agreeing to receipt of study vaccines, ED vaccine availability, receipt of vaccines in the ED, "Yes" and "No" agreeing to follow-up calls and EHR review. See Master Data Flow.

XV. Data Analysis Analysis for Specific Aim I

The primary study comparison is uptake (receipt) of a booster vaccine at any vaccination location within 30 days of the index ED visit, comparing participants seen on Intervention M dates with those seen on Control (No Messaging, No Vaccine Acceptance Question) dates to test our study hypothesis: *Implementation of PROBOOSTVAXED trusted messaging platforms in EDs will be associated with increased booster vaccine uptake in vaccinated ED patients*. This outcome will be ascertained by either review of a participant's EHR 30 days after their index ED visit or a follow-up phone call.

There are three secondary comparisons for Specific Aim I:

- 1) Comparison of 30-day booster vaccine uptake between the Intervention M and Intervention Q arms
- 2) Receipt of a booster vaccine during the index ED visit, comparing participants seen on Intervention M dates with those seen on Control dates - ascertained by check of the participant's EHR on the day after their ED visit

Outcomes will be compared using mixed logistic regression with a fixed effect for randomization assignment, a normally distributed random effect to allow for clustering by enrolling center, and restricted cubic splines to allow for secular trends during the study period. The treatment effects

will be tested by the coefficient for the fixed effect of study arm along with 95% confidence intervals.

Analysis for Specific Aim II

For Specific Aim II, we will compare outcomes in participants seen on Intervention M arm dates with those seen on Intervention Q arm dates to test our study hypothesis: *Implementation of PROBOOSTVAXED trusted messaging platforms in EDs will be associated with increased booster vaccine acceptance in vaccinated ED patients.*

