The outcome is booster vaccine acceptance (defined as a response of "yes" to the question "Would you accept the booster vaccine in the emergency department today if your doctor asked you?"). This outcome will be compared using mixed logistic regression with a fixed effect for randomization assignment, a normally distributed random effect to allow for clustering by enrolling center, and restricted cubic splines to allow for secular trends during the study period. The treatment effects will be tested by the coefficient for the fixed effect of study arm along with 95% confidence intervals.

Analysis for Specific Aim III

For Specific Aim III, the outcome is uptake (receipt) of a booster vaccine at any vaccination location within 30 days of the index ED visit. We will compare outcomes in participants seen on Intervention Q arm dates with those seen on Control dates to test our study hypothesis: Implementation of an ED protocol in which patients are asked whether they will accept a booster vaccine (and notifying ED providers when they say they will accept it) will be associated with increased booster vaccine uptake in vaccinated ED patients.

A secondary outcome for Specific Aim III is receipt of a booster vaccine during the index ED visit, comparing participants seen on Intervention Q dates with those seen on Control dates - ascertained by check of the participant's EHR on the day after their ED visit.

Subgroup Analyses

Another focus of this research is on ED patients who lack primary care group, defined on the Intake survey question: "Do you have a regular clinic or doctor for medical care?" We will analyze outcomes according to the binary indicator of having primary care – yes versus no (and unsure).

We will additionally stratify outcomes by study site (representing different regions of the country and different communities), vaccine administration capability, age, gender, primary language, and race/ethnicity.

Subgroups will be tested by adding a subgroup by intervention interaction to the mixed logistic regression. A subgroup will be considered significant if the pairwise intervention by subgroup omnibus test is significant at the 0.05 level.

Rationale for time (1-day unit) cluster and consideration of Alternative Study Designs:

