In the study Overview, we described our rationale for switching from a one-week unit to a oneday unit cluster. Our primary goal with this research is to determine whether real-world implementation of booster vaccine messaging as an ED-site level intervention results in greater acceptance and uptake of booster vaccines in vulnerable ED populations. Each site sees approximately 150-250 patients per day and applying or not applying the intervention (delivery of booster vaccine messaging) for individual patients in this high workflow, rapid patient turnover ED environment is simply impractical. Given that booster vaccine messaging may be seen and received by all patients non-selectively in the EDs, patient level randomization would result in high risk of cross-contamination between intervention and control arms. Therefore, removal of the messaging intervention from the site completely during specified time periods (1-day units) of Intervention Q, and removal of both interventions (messaging and the vaccine acceptance question) during Control days is the optimal approach. Although single switches of turning on the interventions at each site (i.e., stepped-wedge trial design) is easier to enact, changes in general population attitudes over time introduce bias that limit the validity of this trial method. We expect gradually increasing acceptance and uptake of the booster vaccine over time, which would introduce substantial bias toward the intervention. Finally, cost considerations and feasibility limit the number of sites in this trial, negating the potential advantages of a cross-over trial with randomization by sites. These practical and methodological benefits of the 1-day unit cluster RCT far outweigh the smaller sample size and easier analysis with an individual patient unit RCT or a stepped-wedge design.

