Statistical approach: In terms of statistical approach, this is a superiority trial in which we seek to verify our central study hypothesis that provision of booster vaccine messaging will result in greater acceptance and uptake of the booster vaccine. Following the recommendations of Hussey and Hughes, our statistical analyses will focus on comparing the vaccine uptake rates during the time periods when booster vaccine messaging is in place (Intervention M) and when the system is not in place (Control - usual care) using mixed effects logistic models. The outcome of interest is the binary indicators of whether they have received a booster vaccine in the ED (uptake - yes/no). Models will include a normally distributed random center effect (on the logit scale) to accommodate potential within-center characteristics (e.g., case mix, demographics), as well as terms for time and intervention. Hypotheses testing will focus on the statistical significance of the intervention indicator. We will fit the mixed effects models using maximum likelihood and routines in Stata.

We will test our primary hypotheses and analyze outcomes according to the study arm (index visit in Intervention M day versus control day) to which patients were allocated, regardless of whether they received booster vaccine messaging or not - *intention to treat analysis*.

In addition to the effects on *total* vaccine acceptance, we will also examine the effect of booster vaccine messaging on acceptance in patient sub-groups, especially African American and Latinx persons. Booster vaccine messaging may work for one patient sub-group and not others -- these additional analyses will guide future directions and modifications of booster vaccine messaging.

XVI. Data Management Plan

We will manage data using REDCap, hosted by the core site (UCSF) for secure data entry and management. Patient identifiers (medical record numbers and phone numbers) only link will be

to unique study ID numbers, which will be housed in files that are kept separate from other study data. We will develop a detailed data dictionary to ensure consistent standards across sites. We will reduce missing or erroneous data using the REDcap data quality tool.

XVII. Sample Size Considerations

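### Aim I credits messaging with the M versus Control difference in 30-day uptake, but that contrast tests messaging, acceptance question and provider notification together

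*Combined protocol and SAP*

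**What the plan says.** **Hypothesis.** Specific Aim I in the overview states: "Implementation of PROBOOSTVAXED trusted messaging platforms in EDs will be associated with increased 30-day booster vaccine uptake in vaccinated ED patients". Section XV repeats it in nearly the same words. Under Statistical approach, the plan calls this "our central study hypothesis that provision of booster vaccine messaging will result in greater acceptance and uptake of the booster vaccine". Section IX defines messaging as three items: a video, a printed sheet and a scripted message from the provider. The acceptance question is not among them.

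**Primary contrast.** Section XV tests the hypothesis by "comparing participants seen on Intervention M dates with those seen on Control (No Messaging, No Vaccine Acceptance Question) dates to test our study hypothesis". Statistical approach describes the same contrast as uptake "during the time periods when booster vaccine messaging is in place (Intervention M) and when the system is not in place".

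**What M contains.** The study-arms table gives M both messaging and the acceptance question, and Control neither. The rationale for the one-day cluster refers to "removal of both interventions (messaging and the vaccine acceptance question) during Control days". Section XI adds a step in M and Q at sites able to vaccinate: "when a participant says they will accept the vaccine, the CRC or research staff will ask the participant if it is okay to notify" the provider. It continues: "If participants agree to notification of the ED provider, research staff will notify the ED provider that they stated they will accept the vaccine".

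**The other component.** Aim III compares Q with Control on 30-day uptake. Its hypothesis in Section XV is that asking the question ("and notifying ED providers when they say they will accept it") increases uptake.

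**Where messaging is isolated.** Aim II compares M with Q, but on stated acceptance. For 30-day uptake, M versus Q is the first secondary comparison listed under Aim I. Section XVII sizes only M versus Control.

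**The concern.** The hypothesis names one component, but the arms compared differ by two at every site and by a third where vaccine is available. The plan itself regards the additional part as active, since Aim III predicts that it raises the same endpoint. If Aim III is right, part of the M versus Control difference does not come from messaging, and the primary test cannot say how much.

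Nothing in the plan makes the Aim I conclusion depend on M versus Q. Read as written, a significant M versus Control result confirms a hypothesis about messaging even if M and Q have the same uptake. EDs could then adopt videos, flyers and scripts whose added effect on uptake was never shown, when asking the question and telling the provider might have given the same gain.

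**Working it through.** **Inputs from Section XVII.** Control uptake 5%; target increase 7 points (to 12%); alpha 0.05; power 0.80; 248 per arm; formula for individual randomization. Sidedness is not stated, but the two-sided form reproduces the plan's figure.

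**Assumed input.** The documents give no uptake rate for Q, so a range is used.

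**1. The plan's own figure.** With p̄ the mean of the two rates:

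n = [1.96·√(2p̄(1−p̄)) + 0.8416·√(p₁(1−p₁) + p₂(1−p₂))]² / (p₂−p₁)²

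For 5% and 12%: (0.7730 + 0.8416 × 0.3913)² / 0.07² = 247.98, so 248 per arm and 3 × 248 = 744. This matches. The sample size is correct for M versus Control.

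**2. Primary test when messaging adds nothing (M = Q).**

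Power = Φ{[|p₂−p₁|·√n − 1.96·√(2p̄(1−p̄))] / √(p₁(1−p₁) + p₂(1−p₂))}

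For M = Q = 12% against Control 5%: (1.1024 − 0.7730)/0.3913 = 0.842, and Φ(0.842) = 0.80. The third column is a simulation (one million trials per row, independent binomial arms of 248, two-sided 0.05 tests). It gives the chance that M beats both Control and Q, so that messaging would be wrongly credited under a rule requiring both. The last column is 1.96·√(2p(1−p)/248).

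| M = Q | M vs Control significant | M beats Control and Q | 95% CI half-width, M − Q |
|---|---|---|---|
| 7% | 0.15 | 0.013 | 4.5 points |
| 8.5% | 0.34 | 0.020 | 4.9 points |
| 10% | 0.56 | 0.023 | 5.3 points |
| 12% | 0.80 | 0.025 | 5.7 points |

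At M = Q = 6%, the chance of a significant primary result is about 0.07.

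**3. Power of the contrast that isolates messaging (M versus Q, 248 per arm).** Example, M 12% and Q 7%: (0.05 × √248 − 0.8127)/0.4132 = (0.7874 − 0.8127)/0.4132 = −0.061, and Φ(−0.061) = 0.48. The last column is the simulated chance that M beats both Control and Q.

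| Q | M | Power, M vs Q | n per arm for 80% | Both tests favor M |
|---|---|---|---|---|
| 7% | 12% | 0.48 | 539 | 0.44 |
| 8.5% | 12% | 0.25 | 1,178 | 0.24 |
| 10% | 12% | 0.11 | 3,841 | 0.10 |
| 7% | 14% | 0.72 | 300 | 0.71 |
| 8.5% | 15.5% | 0.67 | 338 | 0.67 |
| 10% | 17% | 0.63 | 373 | 0.63 |

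The first three rows split the planned 7-point gain between the question and messaging. The last three give messaging a full 7 points on top of Q.

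**The case against.** The plan is open about its arms. M is labelled as messaging plus question wherever the contrast is defined, and Control as having neither. All three pairwise uptake contrasts are planned, so the effect of messaging on uptake can be estimated, and Section XV already provides 95% confidence intervals. Comparing a full program with usual care is a legitimate pragmatic primary analysis. No passage says that M versus Q will be ignored in reporting. The Q-arm rates are assumed, and notification happens only at some sites, after a yes and with permission, so the question's effect could be small. At M = Q = 6% the primary test would rarely be significant. A rule requiring M versus Q also costs power when messaging does work: with Q at 5% and M at 12%, the chance of a messaging claim falls from about 0.81 to 0.71.

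Much of this stands. M versus Control is a valid test of the package, no estimate or sample size is wrong, and the loss of power under the rule is real. What it leaves untouched is the stated conclusion. The Aim I hypothesis, the central hypothesis and the description of the primary contrast all name messaging alone, and the listed secondary does not condition any of them. Clear arm labels do not change which hypothesis a significant result is said to confirm. Rewording alone would remove the mismatch for Aim I. The rule is still needed to say what would support a claim about messaging and uptake, which the plan calls its central hypothesis.

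**Conclusion.** The concern holds and should be fixed. The primary contrast supports a conclusion about the package (messaging, acceptance question, and provider notification where vaccine is available), while the hypothesis attributes the effect to messaging. If messaging adds nothing to uptake, the primary test would still be significant with probability 0.15 to 0.80 when M and Q lie between 7% and 12%. Requiring M versus Q as well reduces wrong attribution to 0.013 to 0.025.

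These figures rest on assumed Q-arm rates, 5% in Control, 248 per arm, and independent participants as in the plan's own formula; no clustering adjustment is made. The mismatch itself follows from the text and does not depend on those rates.

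The trial has limited ability to isolate messaging on uptake. Because the interval for M minus Q would be about ±4.5 to ±5.7 points in these cases, a non-significant M versus Q would not show that messaging has no effect.

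**What to change.** 1. In Specific Aim I, Section XV and Statistical approach, restate the hypothesis and conclusion as the effect of the full package (messaging, acceptance question, and provider notification where available) against usual care.
2. State that an effect of messaging on 30-day uptake will be claimed only if M versus Q on that endpoint also favors M at the 0.05 level.
3. Report M versus Q with its 95% confidence interval beside the primary result. Describe a non-significant result as an effect not shown, not as no effect.
4. Keep Q versus Control for Aim III as planned.

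The cost is wording and one claim rule. The Aim I test, Aims II and III, the arms and the sample size do not change. The downside is a narrower primary claim and a modest chance of a messaging claim on uptake: 0.10 to 0.44 if M is 12% and Q is 7% to 10%, and 0.63 to 0.71 if messaging adds a full 7 points over Q at 7% to 10%.

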Recognizing the ED as a unique opportunity to address COVID-19 booster vaccine hesitancy in underserved populations, we will launch the PROmotion of COVID-19 BOOSTer VA(X)ccination in the Emergency Department (PROBOOSTVAXED) trial as an extension of the PROCOVAXED trial, seeking to increase COVID-19 booster vaccine acceptance and uptake among vaccinated ED patients. Because of Omicron variant-associated surges during the COVID-19 pandemic with corresponding research staff illness and ED overcrowding, we found

wide week-to-week fluctuations in enrollment in the PROCOVAXED study. To reduce this variability of enrollment, we have changed the unit of randomization from 1-week to 1-day in the PROBOOSTVAXED trial.

IMPORTANT CHANGE: Under intense political pressure and in response to Congress' reluctance to spend more on COVID-19 pandemic relief, the Biden administration recently made two announcements: 1) the national public health emergency declaration regarding the COVID-19 pandemic will be left to expire as of January 11, 2023, and 2) the administration will end their provision of free COVID-19 vaccines, testing and therapeutics, shifting the costs for vaccines, testing and treatments to health insurers and patients via commercial payment mechanisms. Because of these changes in reimbursement, we have been informed that only some of the PROBOOSTVAXED study sites will have COVID-19 vaccines available for distribution in the ED, whereas others will not. Nevertheless, we will proceed with the same research protocol, however, we will be performing additional subgroup analyses that compare 30-day vaccine uptake in sites with available COVID-19 vaccine to those without for the intervention and control arms.

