The primary outcome for Specific Aims I and III is **30-Day COVID-19 Booster Vaccine Uptake**, which will be ascertained by review of ED electronic health records (EHRs) at 30 days and follow-up phone calls. For Specific Aim I, this primary outcome will be compared between the Intervention M arm (Messaging + Vaccine Acceptance Question) and the Control arm (No Messaging, No Vaccine Acceptance Question). For Specific Aim III, this primary outcome will be compared between the Intervention Q arm (Vaccine Acceptance Question, No Messaging) and the Control arm (No Messaging, No Vaccine Acceptance Question).

Primary Outcome for Specific Aim II: Booster Vaccine Acceptance in the ED

The primary outcome of Specific Aim II is **COVID-19 Booster Vaccine Acceptance** in the ED, which will be ascertained by a survey question of study participants in the ED. This outcome will be compared between the Intervention M arm (Messaging + Vaccine Acceptance Question) and the Intervention Q arm (Vaccine Acceptance Question, No Messaging).

II. IRB

We will submit our protocol to the UCSF Committee on Human Research as a modification. We will continue with multi-site reliance mechanism for the PROCOVAXED study as per NIH guidelines for randomized trials.

III. Deposition of Protocol into ClinicalTrials.Gov

As per federal regulations, we will deposit our full study protocol into the repository https://clinicaltrials.gov/.

IV. Setting and Sites

We will conduct this over six months (mid-September 2023 to February 28, 2024) at five high-volume EDs in four cities: (Zuckerberg San Francisco General, UCSF Parnassus Medical Center [San Francisco, CA], Thomas Jefferson University Hospital [Philadelphia, PA], Ben Taub Hospital [Houston, TX], Duke University Medical Center [Durham, NC]). We have chosen this time-period to coincide with typical waves of the COVID-19 pandemic.

V. Randomization

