Sites will be assigned be assigned to a condition for a day. Randomization within each of the site uses pseudorandom number to permute blocks of time. The blocks consist of 15 days duration during which each condition appears for 5 days. Hence, in any 15 day period there will be a balance of interventions within each of the sites. The particular days of each week (Monday, Tuesday, Wednesday, Thursday and Friday) for each of the study arms will thus vary randomly. This randomization scheme will minimize secular trends (changes in perceptions about the booster vaccine that may occur through the course of various pandemic waves). We

will generate a full study calendar based on this randomization scheme. To try to maintain masking of allocation, sites will be given a blacked-out study calendar and will be instructed to open the calendar for a particular study day the morning of that study day (other than that study day, the rest of the calendar will remain blacked out).

VI. Site Orientation and Training

The Core UCSF Site will develop orientation materials to familiarize the ED Sites with the study protocol. Each site will employ one or more Clinical Research Coordinators (CRCs), who will report to the Site PI and be responsible for day-to-day study implementation. We will develop and disseminate a manual of operating procedures (MOP) with standard personnel training methods, including education kits with scripts, summary cards, and PowerPoint presentations to assist coordinators in the orientation of site clinicians and other staff to our study protocol. We will convene ZOOM conference calls to review this summary and develop plans for optimization of PROBOOSTVAXED messaging platforms to improve usability and workflow. We will refine procedures with updates delivered to the site PIs during weekly ZOOM conferences.

VII. Study Hotline and Quality Assurance

We will maintain a study hotline and encourage study personnel to contact the PI and Central Study Coordinator for all issues and queries. Hotline hours will be during primary study hours (weekday 8 a.m. to 5 p.m. PST).

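### Arms are randomized by site-day, but no written model accounts for the site-day; at the density implied by 744 participants, uptake shows no type I inflation and acceptance a small one

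*Combined protocol and SAP*

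**What the plan says.** The randomized unit is clear. The opening overview says "we have changed the unit of randomization from 1-week to 1-day in the PROBOOSTVAXED trial". Section V (Randomization) permutes days within each site: "The blocks consist of 15 days duration during which each condition appears for 5 days", Monday to Friday only. In Section XV, the rationale for the one-day cluster defends "removal of the messaging intervention from the site completely during specified time periods (1-day units) of Intervention Q", and removal of both components on Control days.

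The analysis models are at another level. Section XV, Analysis for Specific Aim I, has a fixed effect for arm, "a normally distributed random effect to allow for clustering by enrolling center", and restricted cubic splines for calendar time. Aim II repeats this: "This outcome will be compared using mixed logistic regression with a fixed effect for randomization assignment", with the same center effect and splines. The Statistical approach paragraph again has a random center effect with terms for time and intervention. The Aim III paragraph gives an outcome and a comparison but no model.

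Section XVII sizes the trial with formulae for individually randomized patients: 5% versus 12% uptake, alpha 0.05, power of 0.80 or more, 248 per arm. It says that simulation from a mixed model showed this to be conservative. It does not give the levels or variances of that model.

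**The concern.** Patients seen at one site on one day share staff, crowding and vaccine availability, as well as the assigned arm. If their outcomes are correlated for such reasons, that correlation belongs in the standard error of the arm effect. A center intercept does not put it there, because all three arms occur within each center and the center effect largely cancels from the comparison. A smooth spline follows slow trends and does not absorb scatter from one day to the next. The intervals would then be too narrow and the test would reject too often.

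Aim II looks most exposed. Acceptance is a more frequent outcome than uptake, so the same day-level variation on the logit scale gives a larger intraclass correlation (ICC), and the answer is given in the ED that day.

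**Working it through.** **The plan's own figure.** With a two-sided 5% test (sidedness is not stated, but two-sided reproduces the result) and pooled variance under the null:

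n = [1.960·√(2·0.085·0.915) + 0.8416·√(0.05·0.95 + 0.12·0.88)]² / 0.07² = (0.7730 + 0.3293)² / 0.0049 = 247.98, so 248 per arm, with power 0.800.

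**Density.** Section IV gives five sites and "mid-September 2023 to February 28, 2024". From an assumed start on 15 September, with holidays kept, there are 119 weekdays: 119 × 5 = 595 site-days, and 744/595 = 1.25 participants per site-day. Starts from 11 to 18 September give 1.21 to 1.26.

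**ICC (assumed).** For a day SD s on the logit scale, the ICC is roughly s²·p(1−p). Integrating numerically for s = 0.3 and 0.5:
- 5% uptake: 0.0044 and 0.0127
- 12% uptake: 0.0096 and 0.0267
- 43% acceptance: 0.021 and 0.055

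The 43% is 1 − 179/316 from the survey in the overview, which covered never-boosted patients at partly different sites. At 30% or 60% acceptance the ICC range is 0.018 to 0.054.

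**Type I error by formula.** The design effect (DE) is 1 + 0.25·ICC for even daily counts and 1 + 1.25·ICC for Poisson counts. Type I error is 2[1 − Φ(1.96/√DE)].
- Acceptance, Poisson: DE 1.026 and 1.069, giving 5.3% and 5.8%. Even counts: 5.1% and 5.2%.
- Uptake at 5%, Poisson: DE 1.006 and 1.016, giving 5.1% and 5.2%.

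**Type I error by simulation, no day term.** Five sites, 15-day blocks, logistic regression with adjustment for center and time.

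| Setting | SD 0.3 | SD 0.5 | Runs |
|---|---|---|---|
| Acceptance, about 1.25 per site-day, Poisson-like | 5.3% | 6.2% | 12,000 |
| Uptake, same | 4.8% | 4.5% | 12,000 |
| Acceptance, very uneven counts (size-weighted mean 4.7) | 6.1% | 7.7% | 20,000 |
| Uptake, same | 4.6% | 5.0% | 20,000 |
| Acceptance, 5 per staffed day | 6.2% | 8.5% | 3,000 |
| Uptake (8.5%), same | 5.0% | 6.2% | 3,000 |

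Monte Carlo error is about 0.2 points at 12,000 or 20,000 runs and 0.4 at 3,000. Other runs at 1.25 per site-day gave 5.5% and 6.0% (20,000 runs), 5.2% and 5.9% (8,000), and 4.9% and 5.5% (3,000) for acceptance. For uptake they lay between 4.3% and 5.3%. At an extreme SD of 0.8, acceptance reaches about 7% with even counts and 10% with uneven counts.

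**Aim I power.** A test that widens its standard error by √DE has power of 79.5%, 79.0% and 78.5% at ICC 0.01, 0.02 and 0.03 (Poisson). The planned test does not widen it. Its approximate power is Φ[(2.80 − 1.96)/√DE]; even at ICC 0.0267, DE = 1.033 and Φ(0.84/1.017) ≈ 0.796. Simulation agrees: without a day term, power was 80.4%, 79.9% and 79.5% at SD 0, 0.3 and 0.5. A larger set gave 80.2% and 80.1% at SD 0.3 and 0.5.

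**Remedies, acceptance, Poisson counts, SD 0.3 and 0.5.** Uncorrected site-day-clustered errors gave 5.5% and 5.5%. With the Kauermann-Carroll correction and a t reference they gave 4.9% and 4.8%. The data would often put the day variance at zero: in 49% and 29% of runs for acceptance, and 65% and 61% for uptake.

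**The case against.** The strongest reply is that the omission hardly matters. With about 1.25 participants per cluster there is little within-cluster correlation to ignore. Uptake, the primary outcome, shows no inflation in the SD range considered. The Aim II excess is at most about a point and rests on an assumed SD and a borrowed acceptance rate. Corrected site-day errors bring no type I gain for uptake (4.4 to 4.7% against 4.8 to 5.0% without a day term) and cost about a point of power even with no site-day correlation (79.1% to 78.1% in one set of runs). Most of this stands, and it is why replacing the primary uptake analysis should not be mandatory.

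The reply does not remove the gap. The low density is a result of dividing N by the calendar; the plan does not commit to it. Section VIII would approach all eligible patients, and the overview reports wide week-to-week swings in enrolment in the preceding trial. Denser or more uneven enrolment raises the error, most for acceptance.

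A reader might also infer that the sample-size simulation left out the site-day, or that the trial is underpowered. Section XVII supports neither. It is silent on the levels simulated, and the planned analysis keeps about 80% power at SD 0.3 to 0.5. The figures just below 80% describe a test that adjusts for site-day, which is not the test written.

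**Conclusion.** The gap is real and minor. The randomized unit appears in none of the written models, and Aim III has no stated model. At the back-calculated density of about 1.25 and an assumed day SD of 0.3 to 0.5, uptake shows no type I inflation and acceptance runs at about 5.3 to 6.2% instead of 5%. These sizes depend on assumptions about SD, acceptance rate and spread of daily enrolment that the documents neither confirm nor exclude. A severe loss of validity, a biased effect estimate or a need for more patients does not follow. Nor does the evidence support putting a lower figure in place of the power statement.

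**What to change.** In Section XV (Aims I, II and III and the Statistical approach paragraph), pre-specify that the test and 95% confidence interval for study arm account for site-day, defined as center by study date.

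- Aim II: use site-day-clustered standard errors with a named small-sample correction (for example Kauermann-Carroll with a t reference), five center indicators and the existing spline. Indicators are needed because a random center effect leaves only five independent pieces, so site-day clustering does not fit it directly. Alternatively, use a site-day random intercept with a fallback fixed in advance for non-convergence or a zero variance estimate. Confirm beforehand that the chosen correction can be run in Stata, which the plan names.
- Aims I and III: use the same method, or keep the center model and add the site-day analysis as a pre-specified sensitivity analysis. Write out the Aim III model.
- Section XVII: state whether the simulation included site-day variance and with what values. Leave the power figure as it is.

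The data are already collected: Section XIV has staff "recording the following data for all patients approached: study date, study arm". The costs are SAP wording, some programming, slightly wider intervals, and about 1 to 1.5 points of Aim I power if corrected errors become primary for uptake (79.1% and 78.4% simulated at SD 0.3 and 0.5). No extra enrolment is required.
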